2.15.3 Patient Populations

Interim results may be collected and reported. All data will be analyzed at the end of the study. The primary analysis will be performed by the intention-to-treat approach. Everyone who begins the treatment is part of the study whether he or she completes the study or not. Additional per-protocol analysis may also be performed on subjects who complete the entire clinical trial according to the protocol. The most appropriate method of handling missing values will be chosen based on the trial's goals, endpoints and context.

The analysis of demographic, medical history, and efficacy variables will be based on all patients who are randomized and receive at least one treatment. The analysis of safety data will be based on all patients who are randomized, receive at least one treatment, and have at least some safety data.

2.15.4 Analysis of Demographic and Medical History Variables

Summaries will be prepared for all important demographic and medical history variables. For quantitative variables summaries will include the sample size, mean, median, standard deviation, minimum, and maximum. For these variables the treatment groups will be compared using either a t-test or a Wilcoxon Rank Sum test, as appropriate. For categorical variables the summaries will include the sample size and the number and percent of patients for each outcome. For these variables, the treatment groups will be compared using Fisher's Exact test. Statistical significance will be declared if the two-sided p-value is <0.05 .

2.15.5 Analysis of Efficacy Variables

The primary efficacy variable is blinded evaluation of photographs from baseline to Visit 8 (12-week follow up) with respect to fat reduction. Baseline is defined as the last assessment prior to the first treatment. Photos will be graded and the total and percentage of photos correctly identified will be compiled and analyzed. Correct identification percentages will be calculated for each individual reviewer as well as a summary for all three reviewers. Clinical success of grading will be declared if 80% independent reviewers achieve 80% correct identification of the photos.

The secondary efficacy variables are caliper measurements of fat thickness and subject satisfaction rates. As with the primary efficacy variable the assessment at Visit 8 (12-week follow up) will be primary. The analysis and summaries for caliper measurements will include a pairwise treatment group comparison as well as repeated measure ANOVA analysis. Statistical significance with respect to both the treatment and control group comparisons as well as repeated measures of the treatment group will be declared if the two-sided p-value is <0.05 . For each treatment group and timepoint of the caliper measurements a statistical summary will be completed. The summary will include sample size mean, median, standard deviation, minimum, and maximum. The statistical significance of the mean change from baseline to follow-up for each group as well between the treatment and control will be determined using a paired t-test. Subject satisfaction will be analyzed with standard descriptive statistics which include total number of responses in each category as well as the percentage of responses for each category. Clinical success of subject satisfaction surveys will be declared if at least 80% of subjects respond they are satisfied.

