2.15 Statistical Analysis

2.15.1 Hypothesis

For this study to be considered a success, the following criteria must be met:

1. Correct identification of pre-treatment images when compared to post treatment (12 week) images will be $\geq 80\%$.
2. Caliper measurements show statistically significant improvement on treatment area versus control.
3. The subject satisfaction rates at 12-week follow up visit will be $\geq 80\%$.
4. The side effect profile is acceptable to the Physician as it relates to this type of treatment.

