2.15.2 Sample Size Rationale

The primary outcome will be the change in the subjective assessment of the reduction in fat as assessed by blinded evaluation of photographs taken before and after treatments. The primary endpoint will be defined as the 12-week follow up post final treatment with an objective of 80% correct evaluation. The sample size was determined based on a two-sample t-test with a two-sided significance level of 0.05 and power of 95%. A hypothetical control group would assumedly result in correct identification of follow up pictures 50% of the time, with a standard deviation of 50% resulting from an equal amount of correct and incorrect answers. Our objective of 80% correct average evaluation of post treatment photos with a conservative 20% expected standard deviation. Based on these assumptions it was determined that a total of at least 43 patients would be required for the study to have a successful primary outcome.

One of the secondary outcomes will be the change in fat layer thickness as assessed by caliper measurements before and after treatments. Previous studies have shown a change in caliper measurements of 7.0mm in a treated flank, and 0.7mm change in the control. The maximum standard deviation seen for any measurements (treated or control, baseline or follow up) was 5.8 which is used as an assumed standard deviation for sample size calculations.^v Assuming 0.05 significance level and adjusting for a power of 95%, it was determined that 14 subjects would be needed to have a successful secondary outcome measure.

Another secondary outcome is the subject satisfaction rate. The sample size is calculated similarly to the primary outcome and yields the same results.

Based on these assumptions it was determined that a total of 43 patients would be required for the study, which was the maximum calculated among all the study outcome measures. To allow for minor departures in these assumptions and to account of potential subject dropout it was decided to enroll 68 subjects.

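### The 95% power in 2.15.2 is for 80% against a hypothetical 50%; it is not the chance of meeting the primary success rule in 2.15.5, which with three reviewers requires all three to reach 80%

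*Combined protocol and SAP*

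**What the plan says.** Three sections of the combined protocol and SAP bear on primary success.

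- **2.15.1 Hypothesis** opens its list with "For this study to be considered a success, the following criteria must be met". The first item is "Correct identification of pre-treatment images when compared to post treatment (12 week) images will be" at least 80%. It does not say how three reviewers are combined and does not refer to 2.15.5.
- **2.15.2 Sample Size Rationale** gives the planning basis: "The sample size was determined based on a two-sample t-test with a two-sided significance level of 0.05 and power of 95" per cent. The comparator is imagined: "A hypothetical control group would assumedly result in correct identification of follow up pictures 50% of the time", with an SD of 50%. The treated side is "Our objective of 80% correct average evaluation of post treatment photos", with an SD of 20%. The conclusion is that "a total of at least 43 patients would be required for the study to have a successful primary outcome". Enrolment is then set at 68 to allow for dropout and departures from the assumptions.
- **2.15.5 Analysis of Efficacy Variables** first describes reporting: "Correct identification percentages will be calculated for each individual reviewer as well as a summary for all three reviewers". It then states the rule: "Clinical success of grading will be declared if 80% independent reviewers achieve 80% correct identification of the photos".

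Sections 1.1 (Objectives) and 2.13 fix the number of reviewers at three and give no combining rule. The rule in 2.15.5 is therefore the only one in the plan. Section 2.15.5 plans no test against 50%.

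**The concern.** Section 2.15.2 sets a power of 95% beside an 80% objective and calls the resulting number what a successful primary outcome requires. A sponsor, ethics board or regulator reading it would reasonably take 95% as the chance that the primary endpoint succeeds. Success, however, is defined by reaching 80%, reviewer by reviewer, and not by beating 50%. Where the assumed rate equals the pass mark, the chance of passing cannot be near 95% at any sample size.

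A smaller matter is that 2.15.1 does not point to the rule in 2.15.5, and 2.15.2 speaks of an average. The number of reviewers who must pass has to be worked out from a percentage that three reviewers cannot hit exactly.

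**Working it through.** **1. Reproduce the 43.** Inputs from 2.15.2: rates 0.80 and 0.50, SDs 0.20 and 0.50, two-sided alpha 0.05, power 0.95.

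Normal approximation, per group: n = (1.960 + 1.645)² × (0.50² + 0.20²) / 0.30² = 12.995 × 0.29 / 0.09 = 41.9, so 42.

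Noncentral t with 2n − 2 degrees of freedom: power is 94.6% at 42 and 95.1% at 43 per group. The 43 is reproduced as a per-group number. Because the comparator group is hypothetical, the plan takes it as the total.

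**2. What that 95% measures.** It is the chance of a significant difference from 50%. Under the plan's SDs, significance is reached at these observed rates:

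- n = 43: 0.50 + 1.989 × √(0.29/43) = 0.50 + 1.989 × 0.0821 = 66%
- n = 68: 0.50 + 1.978 × √(0.29/68) = 0.50 + 1.978 × 0.0653 = 63%

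Both lie well below the 80% pass mark.

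**3. The success rule in numbers.** 80% of 3 reviewers is 2.4, so 3 of 3 are needed. Each reviewer needs at least 0.80n correct: 34.4, so 35 of 43; or 54.4, so 55 of 68. A pooled reading would need 0.80 × 129 = 103.2, so 104 of 129; or 0.80 × 204 = 163.2, so 164 of 204.

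**4. Chance of meeting it.** The documents give neither true reviewer accuracy nor between-reviewer correlation. Assumptions: equal accuracy p for the three reviewers, subjects independent, every subject counted has a gradable 12-week pair, and correlation anywhere from 0 to 1.

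For one reviewer, P₁ = P(X ≥ r), with X binomial(n, p) and r = 35 or 55. For all three, the chance is P₁³ if reviewers are independent and P₁ if they agree perfectly. The pooled figure is binomial on 3n readings if independent, and P₁ under perfect agreement.

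| True p | n | All three: independent to perfect agreement | Pooled: independent / perfect agreement |
|---|---|---|---|
| 80% | 43 | 12.5% to 50% | 48% / 50% |
| 80% | 68 | 12.5% to 50% | 49% / 50% |
| 85% | 43 | 53.7% to 81.3% | 93.1% / 81.3% |
| 85% | 68 | 65.3% to 86.7% | 97.0% / 86.7% |
| 90% | 43 | 92.9% to 97.6% | 100.0% / 97.6% |
| 90% | 68 | 98.0% to 99.3% | 100.0% / 99.3% |

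At p = 80%, P₁ = 0.50 at both sizes, and 0.50³ = 0.125. Between the two ends, beta-binomial simulation at p = 80% and n = 68 gives about 19%, 25% and 33% for correlations of 0.25, 0.50 and 0.75, and about 43-44% at 0.95.

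**5. Accuracy needed for a real 95% chance.** Solving for p under the all-three rule gives 88.6% (perfect agreement) to 90.6% (independent) at n = 43, and 87.1% to 88.8% at n = 68.

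**The case against.** The best defence is that 2.15.2 is correct for the comparison it describes. It names its test, comparator and SDs, its number is reproduced, and it never says outright that 95% is the probability of observing 80% or more. The roughly one-in-two figure at a true 80% is nearly automatic once the assumed rate equals the threshold, and real accuracy may well be higher. All of this stands. It does not remove the problem: 2.15.2 presents the calculation as what primary success requires, the 80% is the plan's own planning rate, and the comparison that was powered is not among the planned analyses.

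A reader might infer three stronger things that the documents do not support.

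- *That 2.15.1 and 2.15.5 contradict each other.* Only 2.15.5 says how reviewers combine, and it is pre-specified. No section sets a pooled pass mark. The average in 2.15.2 is the mean that a t-test needs as input. Satisfaction is handled in the same way, with a short criterion in 2.15.1 made operational in 2.15.5. Meeting the all-three rule also always meets a pooled 80%, so the stricter rule binds if both are applied. What remains is mainly a missing cross-reference.
- *That the chance of success is one in eight.* That is the lower bound, for three uncorrelated reviewers. Trained dermatologists viewing the same pairs are likely to be correlated, and the figure rises to 50% under perfect agreement.
- *That the trial is too small or likely to fail.* At a true 90% and 68 subjects the rule is met 98-99% of the time. At a true 80%, more subjects would not help.

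**Conclusion.** The point holds as a power statement that does not describe the plan's success rule. The 95% is the power to distinguish 80% from a hypothetical 50%. At the plan's own 80%, the chance of meeting the all-three rule is 12.5% to 50%, and about 48-50% on a pooled reading, at either sample size. The gap from 95% therefore does not depend on which reading is taken.

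The shortfall depends on the true rate. With 68 gradable pairs it narrows to 65-87% at 85% and disappears at 90%. These ranges assume equally accurate reviewers and cover every correlation from 0 to 1; neither quantity is given in the documents. Aligning the wording of the rule across 2.15.1 and 2.15.5 is worthwhile but secondary.

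**What to change.** Make these changes before any photographs are graded.

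1. **2.15.2:** state that the 95% refers to 80% against a hypothetical 50% and is not the chance of primary success. Add the chance of meeting the 2.15.5 rule at the planned size, for a stated range of true accuracy and of reviewer correlation from 0 to 1. The table above can serve as a start.
2. **2.15.5:** replace the percentage of reviewers with a plain statement that all three reviewers must each reach 80%, and label the three-reviewer summary as descriptive.
3. **2.15.1:** refer to the rule in 2.15.5.

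If the sponsor intends a pooled rule instead, that is its choice and the fix does not require it; the pooled rule should then be stated in both 2.15.1 and 2.15.5 before grading.

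The cost is a few sentences and one short calculation, with no new data and no change to the sample size. The drawback is that the stated chance of success becomes less favourable than the 95% now implied.

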2.6 Pre-Treatment Procedures

If the subject is of childbearing potential (i.e. females not post-menopausal or not surgically sterile), they will be asked if they are pregnant, the date of their last menstrual cycle, and perform a urine pregnancy test. A urine pregnancy test will be performed on all women of childbearing potential prior to each treatment. A urine pregnancy test may also be conducted at the Investigator's discretion at any time during the study. If a urine pregnancy test is conducted, then a negative result must be obtained within 24 hours prior to the treatment.

Urine Pregnancy Test Procedure:

- A urine sample is tested mid-stream or by cup sample with an indicator stick.
- Negative results are indicated on the indicator stick.

- The area to be treated will be identified and may be marked with a surgical marker.
- Caliper measurements of both flanks will be taken prior to the first treatment and prior to treatment 4 and may be taken prior to other treatment visits as well.
- Photographs will be taken prior to the first treatment and prior to treatment 4 and may be taken prior to other treatment visits as well.
- The treatment area and the neutral pad area may be cleansed with water and soap and/or an alcohol wipe.
- The neutral pad will be placed on the back in an area determined by the Investigator to maintain standard energy settings and to require less power from the device during the treatment.

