2.16 Randomization

One flank will receive treatment with the TempSure® Firm handpiece and the other will not receive treatment to serve as a control. Randomization will occur using a validated method determined by the Investigator, such as flipping a coin or an electronic system such as Virtual Coin Toss (www.virtualcointoss.com).

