ASSESSMENT OF UNCERTAINTY:

There is uncertainty of the efficacy of the treatment when TempSure® Firm is used for the treatment of unwanted fat.

CONCLUSION:

The TempSure® Firm handpieces used in this study have not been FDA cleared for use for the treatment of wanted fat (lipolysis) but pose no more risk than the currently cleared indications for use.

A previous safety study, CYN18-RF-TISSUE-RD, was conducted using excised human abdominoplasty tissue to test various radiofrequency parameters with the 60mm handpiece. Another safety study, CYN19-TS-ABDOM, was conducted using patients scheduled for an abdominoplasty surgery to use in-vivo tissue to test various radiofrequency parameters with the 60mm handpiece. Thermal measurements of treatment zones were collected to evaluate the depth of penetration and effects on human tissue.

Studies CYN17-RF-CLINIC and CYN19-TS-ENVI-ABD collected safety and efficacy data using the 25mm, 30mm, and 60mm handpieces on various body areas, including the abdomen.

Patient population to be enrolled in this clinical study:

Total anticipated population: 68 Subjects

Age Range years old: 18 – 55 years old

Gender: Male or Female

Condition: Unwanted fat on flanks

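### The paired t-test on caliper change is valid but fixes the baseline slope at 1; estimating that slope could narrow the treated-versus-control interval at almost no cost

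*Combined protocol and SAP*

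**What the plan says.** Section 2.15.1 lists as the second success criterion: "Caliper measurements show statistically significant improvement on treatment area versus control".

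Section 2.15.5 makes the 12-week visit primary for calipers. The caliper analysis "will include a pairwise treatment group comparison as well as repeated measure ANOVA analysis". For mean change from baseline, significance within each flank "as well between the treatment and control will be determined using a paired t-test", at two-sided 0.05. No baseline covariate is named for either analysis.

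The data for an adjusted analysis are already collected. Section 2.6 states: "Caliper measurements of both flanks will be taken prior to the first treatment". Sections 2.9 and 2.12 repeat the measurement at 6 and 12 weeks. Section 2.16 assigns the treated side at random within each subject.

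Section 2.15.2 sizes the caliper outcome on changes of 7.0 mm (treated) and 0.7 mm (control). For the spread it says: "The maximum standard deviation seen for any measurements (treated or control, baseline or follow up) was 5.8". With 95% power it arrives at 14 subjects. The overall requirement is 43, and 68 are to be enrolled.

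**The concern.** A change score forces the baseline flank difference to carry through to week 12 with a slope of exactly 1. Skinfold readings contain measurement error, so part of any baseline difference between flanks may not persist, and the true slope may then be below 1. In that case the change score adds baseline noise that a regression would remove.

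What is at stake is the width of the interval for the treated-versus-control effect. The power for criterion 2 is also at stake if the true effect is well below the planned one. That is possible: the planning effect comes from a cited cryolipolysis study, and section 3.3 says of the present device: "There is uncertainty of the efficacy of the treatment when" it is used on unwanted fat.

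**Working it through.** **Inputs from the documents.** Effect 7.0 − 0.7 = 6.3 mm; SD 5.8 mm; two-sided 0.05; power 95%; 14, 43 and 68 subjects (2.15.2, 2.15.5).

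**Inputs assumed.** r, the correlation between the baseline and week-12 flank differences; k, the week-12 SD of that difference over its baseline SD; and a smaller effect of 2 mm, as an illustration.

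**The plan's own figure.** A paired t-test (noncentral t) with 6.3 mm and SD 5.8 has power 94.8% at n=13 and 96.3% at n=14. The stated 14 therefore reproduces, and it treats 5.8 mm as the SD of the within-subject change difference. That reading is used below. The planned half-width is then t × 5.8/√n: about 1.77 mm at n=43 and 1.40 mm at n=68.

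**Same target.** Let D0 and D12 be treated minus control at baseline and at week 12. Random side assignment gives D0 an expected value of zero. The mean of D12 − D0 and the intercept from regressing D12 on D0 (not centred) therefore estimate the same effect.

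**Variance.** With s the baseline SD of the difference:
- change score: s²(1 + k² − 2rk)
- adjusted: s²k²(1 − r²)
- ratio, adjusted over change: k²(1 − r²)/(1 + k² − 2rk) = 1 − (1 − rk)²/(1 + k² − 2rk)

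At k=1 the ratio is (1 + r)/2. The second form shows that it never exceeds 1 and equals 1 exactly when rk = 1, that is, when the true regression slope is 1. Estimating the slope inflates the variance by about 1/(n − 3): 1/40 = 2.5% at n=43 and 1/65 = 1.5% at n=68.

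**Example.** k=1, r=0.5, n=68: 1.997 × 5.8 × √[(0.75/68)(1 + 1/65)] = 1.22 mm.

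**Results.** Half-widths are averages over simulated trials (40,000 per setting) and agree with the formula to about 0.01 mm.

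| k | r | rk | Variance ratio | Half-width, n=68 (paired t 1.40 mm) | Power at 2 mm, n=43 (paired t 60%) |
|---|---|---|---|---|---|
| 0.8 | 0.5 | 0.40 | 0.571 | 1.07 mm | 82% |
| 1 | 0.3 | 0.30 | 0.650 | 1.14 mm | 77% |
| 1 | 0.5 | 0.50 | 0.750 | 1.22 mm | 71% |
| 1 | 0.7 | 0.70 | 0.850 | 1.30 mm | 66% |
| 1 | 0.9 | 0.90 | 0.950 | 1.37 mm | 61% |
| 1.2 | 0.5 | 0.60 | 0.871 | 1.31 mm | 65% |
| 1.2 | 0.7 | 0.84 | 0.966 | 1.39 mm | 60% |
| 1.2 | 0.8 | 0.96 | 0.997 | 1.41 mm | 59% |
| 1.4 | 0.7 | 0.98 | 1.000 | 1.41 mm | 59% |

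With no effect, both tests rejected in about 5% of trials in every setting. At 6.3 mm both exceed 99% power at n=43 and at n=68.

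**The case against.** The strongest case is that nothing here is wrong. A paired t-test on within-subject change is a standard split-body analysis, it holds its error rate, and the sample size reproduces with exactly this test. All of that stands.

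The gain also rests on values the documents do not supply. At SD 5.8 mm the planned test keeps 95% power down to about 3.3 mm at n=43 and 2.6 mm at n=68, so the effect could fall by about half without material loss. Section 2.15.2 describes 5.8 mm as the SD of single measurements. If so, an assumed left-right correlation of 0.8 with r=0.5 and k=1 gives a change-difference SD of 5.8 × √0.4 × √1 = 3.67 mm. Power for 2 mm at n=43 is then already about 94%, against 98% adjusted. This stands too, and it keeps the point small. Nor does 2.15.5 ask for an interval, so a narrower one is useful only if it is reported; the fix adds it.

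Three stronger readings are tempting and should be resisted.
- A reader might infer that the baselines go unused. They are used, by subtraction; only the slope is at issue.
- A reader might infer that adjustment always helps unless the flank difference is almost perfectly correlated over time. The condition is rk near 1, which r=0.7 with k=1.4 already meets. A k above 1 is plausible when only one flank is treated and sections 2.9 and 2.14 expect some non-responders.
- A reader might infer that the SAP formally assigns criterion 2 to the paired t-test. It does not. Section 2.15.5 also lists a "pairwise treatment group comparison as well as repeated measure ANOVA analysis" and does not say which analysis decides. The paired t-test is simply the only test named for the treated-versus-control change.

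**Conclusion.** The point holds as an optional gain in precision, at the lowest level of severity, and not as an error. With 5.8 mm as the SD of the change difference, the half-width at n=68 goes from 1.40 mm to 1.14-1.37 mm at k=1 (r 0.3-0.9), to 1.07 mm at k=0.8 with r=0.5, and to 1.31-1.39 mm at k=1.2 (r 0.5-0.7). Where rk is near 1 there is no gain, and the loss is about 0.01 mm at n=68 and about 1 point of power or less.

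No decision changes under the plan's own inputs. The protection is for an effect much smaller than planned: at an assumed 2 mm and n=43, power goes from 60% to 61-77% at k=1 (r 0.3-0.9) and to 59-65% at k=1.2 (r 0.5-0.8). The conclusion rests on fair random assignment of the side and on complete week-12 data. Its size rests on r, k and the reading of 5.8 mm, none of which the documents settle.

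**What to change.** In 2.15.5, state that criterion 2 is decided by the intercept, with its 95% confidence interval and two-sided 0.05 test, from regressing the week-12 treated-minus-control caliper difference on the baseline treated-minus-control difference. Leave the covariate uncentred, so that the intercept is the effect for flanks that were equal at baseline. Keep the paired t-test and the repeated-measures ANOVA as supportive analyses. This also settles which caliper analysis decides the criterion.

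The cost is SAP wording and one degree of freedom, with no new data, visits or subjects. Make the change before any between-flank caliper result is examined, since 2.15.3 allows interim results to be collected and reported.
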